4.4 Exclusion Criteria

The following are criteria for exclusion from participating in the study:

1. Uncontrolled systemic disease
2. Females who are pregnant, nursing, or planning a pregnancy, or who are of childbearing potential and not using a reliable means of contraception during the study (see Section 4.5.3)
3. Known allergy or sensitivity to the study medication or its components, any component of the delivery vehicle, or any diagnostic or surgical prep agents used during the study (eg, topical anesthetic, dilating drops, fluorescein, povidone-iodine)
4. Any condition which would preclude the patient's ability to comply with study requirements (including completion of the study)
5. Patients who have a condition or are in a situation, which, in the investigator's opinion, may put the patient at significant risk, may confound the study results, or may interfere significantly with the patient's participation in the study
6. Concurrent or anticipated enrollment in an investigational drug or device study or participation in such a study from 2 months prior to the Baseline visit through the final study visit
7. Previous use of commercially available Bimatoprost SR; concurrent enrollment in another Allergan Bimatoprost SR study; or previous enrollment in which an implant was received. Patients enrolled in the 192024-091/092 studies who were randomized to the control treatment and never received an implant may be considered for enrollment at the investigator's discretion.
8. Known history of bleeding disorder or prolonged bleeding after surgery (in the opinion of the investigator). Note: Patients receiving pharmacologic blood thinners (eg, aspirin, Coumadin) may be enrolled at the investigator's discretion.

Ocular Exclusion Criteria for Both Eyes:

9. History of previous laser trabeculoplasty
10. History or evidence of clinically relevant, substantial ocular trauma (eg, a traumatic cataract, traumatic angle recession, etc)
11. The following surgical history:
 - a. History or evidence of complicated cataract surgery: eg, surgery resulting in complicated lens placement (such as anterior chamber intraocular lens implant [IOL], sulcus IOL, aphakia, etc) or intraoperative complications (such as a posterior capsular tear [with or without vitreous loss], substantial iris trauma, etc).

Note: history of uncomplicated cataract surgery is not an exclusion.
 - b. History of phakic IOL insertion for refractive error correction
12. Intraocular surgery (including cataract surgery) and/or any ocular laser surgery within the 6 months prior to treatment (Day 1)
13. Any history of corneal graft, including partial grafts (eg, Descemet's Stripping Endothelial Keratoplasty [DSEK], Descemet's Membrane Endothelial Keratoplasty [DMEK]); or incisional refractive surgery (eg, radial keratotomy), other than astigmatic keratotomy or limbal relaxing incisions
14. Corneal or other ocular abnormalities that would preclude accurate readings with an applanation tonometer, anterior segment-optical coherence tomography, specular microscope, and/or a contact pachymeter, or could confound study results, eg, moderate to severe corneal dystrophy, including Anterior Basement Membrane Disease (ABMD; ie, Map-Dot-Fingerprint [MDF]) and guttata. Mild ABMD or mild guttata are not exclusionary by clinical examination if, in the opinion of the investigator, the condition is stable and not likely to cause corneal changes during the course of the study.
15. Active or recurrent ocular disease (eg, uveitis, ocular infection, chronic moderate to severe blepharitis or severe dry eye, severe ocular seasonal allergies) or sight threatening diseases (eg, neovascular age-related macular degeneration [ARMD], diabetic macular edema) that, in the opinion of the investigator, would put the patient at a significant risk or would interfere with the interpretation of the study data. Patients with slowly progressive eye diseases (ie, mild cataracts, nonneovascular ARMD) can be enrolled at the discretion of the investigator.

16. Any history of external ocular or intraocular malignancy, and/or any history of benign ocular neoplasia that in the investigator's opinion resulted in clinically significant ocular morbidity
17. History of herpetic ocular diseases (including herpes simplex virus and varicella zoster virus)
18. The following ocular surface findings:
 - a. Bulbar conjunctival hyperemia, on either macroscopic or slit-lamp examination, $> +1$ (mild) at baseline
 - b. Active ocular surface findings other than bulbar conjunctival hyperemia, on either macroscopic or slit-lamp examination, $> +1$ (mild) at Baseline
19. History of moderate or worse ($\geq +2$) bulbar conjunctival hyperemia due to marketed prostaglandin, prostamide, or prostaglandin analog use
20. The anticipated wearing of contact lenses during the study that deviates from the following (contact lens wear is allowed during the study, but is to be temporarily discontinued before study visits, and before and after an Administration Day according to the following):
 - a. Use of soft lenses should be discontinued at least 3 days prior to Baseline, and use of rigid gas permeable or hard contact lenses should be discontinued at least 1 week prior to Baseline
 - b. Use of soft lenses should be discontinued at least 3 days and use of rigid gas permeable or hard contact lenses should be discontinued at least 1 week prior to a scheduled study visit or Administration Day visit
 - c. Use of contact lenses of any kind should be discontinued for 1 week following any Bimatoprost SR (or Sham) administration
21. Central corneal thickness of < 480 or > 620 micrometers
22. Anticipated need for any incisional or laser ocular surgery during the study
23. History of anatomically narrow angle resulting in evidence of angle changes or any history of closed angle glaucoma. Note: historically narrow angled patients whose angle has been opened by cataract surgery or peripheral iridotomy may be eligible for enrollment if they have no evidence of angle abnormalities.
24. History or evidence of a peripheral iridotomy/iridectomy in the inferior iris

25. Any history of trabeculectomy or other types of glaucoma surgery, including a glaucoma seton or aqueous bypass stents
26. Peripheral anterior synechiae (PAS) in the inferior iridocorneal angle on gonioscopic examination at Screening
27. Visual field loss that, in the opinion of the investigator, is functionally significant (eg, split fixation, field defect within the central 10 degrees that is visually significant or likely to cause central visual impairment upon progression) or shows evidence of progressive visual field loss within the year prior to baseline (Note: Two visual fields are required for qualification, 1 performed within the 10 months prior to or at Screening, and 1 performed at baseline or during the washout period using the protocol-required testing method [see Procedure Manual]. The same test methodology should be used for all historical and study-related examination for a given patient.)
28. Evidence of macular edema during screening or in patient's medical history
29. Anticipated use of corticosteroids in either eye (except as described in Section 4.5.1 [Permissible Medications/Treatments]) or systemically during the study, or historical use prior to Baseline within:
 - 3 years: intraocular fluocinolone acetonide
 - 6 months: intraocular corticosteroid(s) other than fluocinolone; any injectable periocular or sub-Tenon's/subconjunctival corticosteroid
 - 2 months: systemic (eg, oral, intramuscular, intravenous) or topical ocular corticosteroids
 - 2 weeks: dermal corticosteroids applied to skin of the eyelid(s), around the eye, or adnexa
30. Anticipated use of other topical ocular medications except as described in Section 4.5.1 (Permissible Medications/Treatments)

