- ⁱ Two visual field tests are required prior to the administration procedure. The first can be performed up to 10 months prior to or at Screening, and the second during Washout or at the Baseline visit. For a given patient, the same test methodology must be used for historical fields and all fields performed throughout the study.

- j [REDACTED] See Procedure Manual for details. Assessment will be repeated at Week 52 and Month 24/Exit and may be performed at any interim study visit at the discretion of the investigator.
- k Biomicroscopy on the SLT Administration Day is performed following treatment as described in Section 8.4.3.1.
- l [REDACTED] See Procedure Manual for details.
- m Screening: patient #; Day 1: **randomization** after eligibility confirmation (may be done at end of Baseline visit if needed); Baseline: H0 IOP

Table 3 Administration Cycle 1 Schedule of Visits and Procedures: Day 4 through Week 15

Visit	Bimatoprost SR Cycle 1 Day 1 Administration	Cycle 1 Day 2 Safety Visit	Cycle 1 Day 4 Phone Call ^a	Cycle 1 Week 2 Phone Call ^a				
	Day 4				Week 4	Week 8	Week 12	Week 15 ^b
Visit Windows	+3 days				±4 days	± 4 days	±4 days	± 4 days
Adverse Events	X	X	X	X	X	X	X	X
Concomitant Medications/ Procedures	X	X	X	X	X	X	X	X
Vital Signs (at rest ≥ 5 minutes)	X	X			X	X	X	X
Ocular Examinations in bold should be performed in the order shown								
Pre-Hour 0 exams (may perform in any order before Hour 0 IOP)								
Macroscopic Conjunctival Hyperemia Assessment ^c		OU			OU	OU	OU	OU
Best-Corrected Visual Acuity ^d		OU			OU	OU	OU	OU
Intraocular Pressure H0	SC/T ^e	OU			OU	OU	OU	OU
Non-contact Exams (may perform in any order at any time before gonioscopy)								
Macroscopic Iris Color Assessment					OU		OU	
Manifest Refraction ^d							OU	
Specular Microscopy					OU		OU	
Biomicroscopy ^c	SC/T ^e	OU			OU	OU	OU	OU
Intraocular Pressure H2 and H8 (selected sites/patients) ^f							OU ^f	
Gonioscopy/Angle Assessment					OU ^g	OU	OU ^g	OU
Pachymetry (may be done any time after gonioscopy)					OU		OU	
Pupil Dilation (may perform post- dilation eye exams in any order)							OU	

Visit	Bimatoprost SR Cycle 1 Day 1 Administration	Cycle 1 Day 2 Safety Visit	Cycle 1 Day 4 Phone Call ^a	Cycle 1 Week 2 Phone Call ^a				
	Day 4				Week 4	Week 8	Week 12	Week 15 ^b
Visit Windows	+3 days				±4 days	± 4 days	±4 days	± 4 days
Dilated Ophthalmoscopy							OU	
Optic Disc Examination							OU	
Contact Interactive Response System ^h	X							

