Specular Microscopy: Endothelial cell density will be assessed using specular microscopy performed on the central cornea at all sites. The determination of central endothelial cell density for study entry as well as study visit measures will be determined by the Reading Center. See the Procedure Manual for further details. The same instrument should be used throughout the study for a given patient. Qualification will remain valid for 1 year after Screening in patients who are not enrolled at the time of Screening, if in the investigator's opinion there have been no clinically significant changes occurring in the eyes (eg, ocular surgery) during that time.

Pachymetry: Corneal thickness using ultrasound (contact) pachymetry will be performed on the central cornea. The same instrument should be used throughout the study for a given patient. Contact pachymetry may be performed any time after gonioscopy. See the Procedure Manual for further details.

Anterior Segment-Optical Coherence Tomography: Anterior segment-optical coherence tomography measurements will be performed at all sites and a Reading Center will be used to examine angle size for investigational purposes. See the Anterior Segment Optical Coherence Tomography Image Acquisition manuals from the Reading Center for further details on the use of optical coherence tomography. In the event that the anterior segment-optical coherence tomography type as specified in the manuals is not available, a suitable alternative may be approved by Allergan and the designated reading center for use. The same instrument should be used throughout the study for a given patient.

Visual Field: Visual field examinations will be assessed using automated perimetry (using either Humphrey 24-2 full threshold program or 24-2 Swedish Interactive Thresholding Algorithm (SITA) Standard, or Octopus G1 or 24-2 and dynamic or normal strategy). The same test methodology must be used throughout the entire study for a given patient. Visual field data may also be submitted to an Allergan designated vendor for additional evaluation.

lymphatic; and skin. The patient's height and weight will be recorded at the Screening visit only.

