11.3.3 Visual Field

Visual field examinations will be assessed by automated perimetry with either the Humphrey Field Analyzer (using a 24-2 full threshold or 24-2 [SITA] Standard program) or the Octopus Perimeter (using a G1 Dynamic or Normal strategy or 24-2 Dynamic or Normal strategy program) at Screening, Baseline, Week 24, Week 52, Month 18, and Month 24/Exit. The same machine type (Humphrey vs. Octopus) should be used throughout the entire study for a given patient. Visual field overall results will be recorded on the eCRF as normal or abnormal. Abnormal findings include enlargement of blind spot, superior arcuate scotoma, inferior arcuate scotoma, paracentral scotoma, nasal step, central scotoma, generalized depression, and temporal scotoma and other. An eye may exhibit multiple abnormalities. Number and percentage of any post-baseline abnormal findings compared with baseline normal findings on visual field will be summarized by eye and by visit regardless of the machine type.

In addition, mean deviation or mean defect (MD) and change from baseline recorded in decibels (dB) will be analyzed by visit and by machine type (Humphrey and Octopus respectively). If the machine type is different between baseline and post baseline visit, no change from baseline will be derived. For patients, whose visual fields were assessed by one machine type as recorded, but there is a missing machine type at a post-baseline visit, the missing machine type will be assumed as the same machine type and the mean deviation or mean defect assessments will be derived.

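### The SAP's check before deriving visual-field MD change covers machine type only, while the protocol requires the same test methodology; a program or strategy switch on one machine would pass unscreened

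*Protocol*

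**What the plan says.** Protocol 6.2 (Safety Measures) lists the permitted tests. On the first machine there are two programs, full threshold and SITA Standard, both with the 24-2 pattern. For the second machine the text reads "or Octopus G1 or 24-2 and dynamic or normal strategy". The sentence that follows this list is "The same test methodology must be used throughout the entire study for a given patient". The footnotes to the schedule tables extend this to earlier fields: "For a given patient, the same test methodology must be used for historical fields and all fields performed throughout the study". Section 8.4.1 repeats the rule for the Screening visit. Exclusion criterion 27 in section 4.4 has the softer form: "The same test methodology should be used for all historical and study-related examination for a given patient".

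SAP 11.3.3 names the same programs and strategies, but its consistency rule is "The same machine type (Humphrey vs. Octopus) should be used throughout the entire study for a given patient". It summarises MD and its change from baseline by visit and separately for the two machines. Its only condition for withholding a change value is "If the machine type is different between baseline and post baseline visit, no change from baseline will be derived". A missing post-baseline machine type is taken to be the patient's known machine, and the value is derived. The separate count of new abnormal findings is made without regard to machine type.

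**The concern.** Where the protocol lists machine, test program and strategy and then demands one methodology per patient, the natural reading is that all three should stay fixed. The SAP guards only the first. A patient tested on Humphrey full threshold at baseline and SITA Standard at Week 52, or on Octopus G1 and later 24-2, would still receive an MD change. That value would contain any difference between the two tests as well as any true change in the field.

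What is at stake is the reading of a long-term safety measure. Fields are taken at Week 24, Week 52, Month 18 and Month 24/Exit in a population that includes glaucoma. The categorical summary compares post-baseline abnormal findings with normal findings at baseline. For an eye already abnormal at baseline, MD change is therefore the main field measure that could show worsening.

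**Working it through.** The plan states no figure on this point, so there is none to reproduce. The check compares the two rules and counts what the SAP condition catches.

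**Inputs (Protocol 6.2; SAP 11.3.3 names the same tests)**
- Humphrey: 24-2 full threshold, 24-2 SITA Standard = 2 combinations.
- Octopus: G1 or 24-2, each with dynamic or normal strategy = 2 × 2 = 4 combinations.
- Total: 2 + 4 = 6.

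**Possible mismatches between baseline and a later visit (ordered)**
- All: 6 × 5 = 30.
- Different machine, change withheld by the SAP: 2 × (2 × 4) = 16.
- Same machine, change still derived: Humphrey 2 × 1 = 2, Octopus 4 × 3 = 12, together 14.
- Check: 16 + 14 = 30. Share passing: 14/30 = 47%.
- Ignoring order: 15 pairs, of which 8 are stopped and 7 pass (1 Humphrey, 6 Octopus).

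This counts kinds of mismatch. It says nothing about how often any of them occurs.

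**Is there another screen?** The per-protocol exclusions in SAP 6.2 concern data for the primary efficacy (IOP) analysis. SAP 11.0 runs all safety analyses on the safety population. SAP Amendments 1 and 1.1 list no change to 11.3.3. No other SAP text conditions MD on program or strategy.

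**Size, on assumptions only.** The documents give no switch rate and no MD difference between programs. Let f be the share of eyes in a machine stratum that switch and δ the difference between tests, with every switch in the same direction. The shift in mean MD change is f × δ:

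| f (assumed) | δ = 0.5 dB | δ = 1 dB | δ = 2 dB |
|---|---|---|---|
| 1% | 0.005 | 0.01 | 0.02 |
| 5% | 0.025 | 0.05 | 0.10 |
| 10% | 0.05 | 0.10 | 0.20 |

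Switches in both directions would partly cancel, so each entry is an upper value for its row and column. For a single eye that switches, the error is the whole of δ.

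**With the condition widened** to machine type, program and strategy, all 30 ordered mismatches would be withheld, provided the items are recorded.

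**The case against.** The strongest reply is that the protocol already controls this at source: a program switch breaches a mandatory rule, and nothing in the documents suggests that such breaches are expected. It is right that the problem needs a site deviation. It does not settle the matter, because a machine switch breaches the same rule and the SAP still provides for it.

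A second reply is that neither document defines test methodology, and criterion 27 refers to the Procedure Manual for the testing method. That stands as a limit. The position of the rule in Protocol 6.2, straight after the programs and strategies, supports the wider reading without proving it.

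Third, the machine check may exist because the two machines report differently named indices (mean deviation, mean defect), whereas the index on one machine keeps its name. No passage says that MD differs between programs of one machine. This is a plausible reason for the SAP's choice, and it is why the size must be left open. A shared index name does not show that the tests are interchangeable, and the protocol's rule suggests caution.

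Fourth, the documents show machine type, MD and the overall result as recorded items, but do not show that program or strategy is in the database. This stands and shapes the fix.

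A reader might also infer that the SAP loosens what sites must do, or that a test switch would be declared progression. The documents support neither. The SAP does not govern site conduct, and it attaches no test, loss threshold or decision rule to MD.

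**Conclusion.** The mismatch is real and minor. The SAP's derivation rule is narrower than the protocol's requirement: 14 of 30 possible ordered mismatches would yield an MD change that the protocol's rule gives reason to distrust. The count rests on reading test methodology as machine, program and strategy together.

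The effect is conditional on a site deviation, and its frequency and size are unknown. The range of 0.005 to 0.2 dB in a group mean is illustrative and rests wholly on assumed inputs.

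It would be tempting to conclude that the comparison of Bimatoprost SR with SLT is biased. The documents do not support that. The rule applies per patient, so a switch would probably affect both eyes of that patient, and most of the shift would cancel between eyes. What is distorted is the level of change in the individual eye and its spread. The primary IOP analysis does not use MD.

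**What to change.** In SAP 11.3.3, replace the machine-type condition with one along these lines: *MD change from baseline is not derived at a visit where machine type, program or strategy is recorded and differs from baseline; such cases are listed as protocol deviations.* Reword the SAP's consistency sentence to use the protocol's term, test methodology, and say that it means machine, program and strategy.

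Where program or strategy is not recorded, keep the MD change but report the number of such records by visit. Simply extending the existing missing-machine assumption to a missing program would let every such record pass as a confirmed match, which could leave the check empty.

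The cost is a short SAP edit, an added condition in the derivation, a listing, and a few MD changes set to missing. It requires no protocol change. It does depend on program and strategy being available in the data, which should be confirmed first. If they are not, the SAP should state that only machine type can be verified.

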4.5 Permissible and Prohibited Medications/Treatments

4.5.1 Permissible Medications/Treatments

Ophthalmic Medications/Treatments

Intermittent use of artificial tear products is allowed if they are taken > 15 minutes before any study procedure or if they are required for a study procedure. Intermittent use of ocular decongestants or antihistamines is allowed if not taken within 2 days prior to a scheduled visit.

Use of artificial tear products and ocular decongestants or antihistamines may be restarted 3 days after any study administration (Bimatoprost SR, Sham Bimatoprost SR, SLT, or Sham SLT) procedure.

Note: post-procedural use of artificial tear products following SLT/Sham SLT administration is allowed at the investigator's discretion; patients should be instructed to wait at least 15-20 minutes after instilling required medication (eg, NSAID) drops before instilling artificial tear products. Use of artificial tears is not allowed following Bimatoprost SR/Sham Bimatoprost SR administration except as described above (restart 3 days after).

Use of post-Bimatoprost SR administration topical ocular antibiotics for 3 days, and corticosteroids or nonsteroidal anti-inflammatory drugs (NSAIDs) for up to 7 days following the administration days is permissible.

Use of immediate pre- and post-SLT topical ocular antihypertensive medication (ie, brimonidine or apraclonidine) is permissible. Post-SLT topical NSAIDs are also permissible for 3 days following the procedure. The medications instructed for use pre- and post-SLT are described in detail in Section [5.9.2](#).

Systemic Medications

Systemic beta-blocker containing medications are permitted, provided that the dose/dosing regimen has remained stable for at least 2 months prior to screening and is not anticipated to change during the duration of the study.

The use of systemic NSAIDs is also permitted.

In addition, therapy considered necessary for the patient's welfare may be given at the discretion of the investigator. If possible, the concurrent therapy (ocular and systemic) administered should not have an effect on study outcomes. However, if concurrent medications may have an effect on study outcomes, these medications should be administered in dosages that remain constant throughout the duration of the study. If the permissibility of a specific medication/treatment is in question, please contact Allergan.

In the unlikely event that the Bimatoprost SR implant requires removal for significant safety reasons, this may be performed at the discretion of the investigator following a discussion with the medical safety physician at Allergan as needed (see Procedure Manual for details).

Note that in the event that the investigator performs an unanticipated incisional surgical procedure on the Bimatoprost SR implanted eye during which ocular fluid is to be removed, ocular fluid/implant samples may be collected for analysis at the investigator's discretion (see Procedure Manual for details).

